Table 1. Contraindications to BoNT injection of the bladder

 • Presence of infection at proposed injection site • Known hypersensitivity to BoNT toxin preparation or any components in the formulation • Urinary tract infection • Urinary retention • Post void residual > 200ml in patients NOT routinely performing clean intermittent self-catheterization (CISC) • Patient unwilling or unable to use CISC • Patient unable to discontinue anti-platelet therapy for 3 days prior to injection • Anti-coagulation therapy that cannot be adjusted for the procedure • Non-compliance with prophylactic antibiotics

Onset of action is 2-4 weeks with and expected treatment duration of 42-48 weeks. Injection can be repeated as needed as soon as 12 weeks after injection. Clinical follow-

up is recommended 1-2 weeks following the procedure and again at 2-3 months [26, 27].

BoNT injection of the bladder can be performed under general anesthesia, but in its most cost-effective form it is administered an in-office procedure [7]. Though studies have evaluated patient satisfaction with results of in-office treatment, limited data exist to guide optimum pain management during injection [9, 10].

B&O suppositories (NDC-054-7045-12 and NDC-0574-7040-12, Case# 665219) have been commonly administered to treat spastic lower urinary tract pain. B&O combines the anti-muscarinic properties of a naturally occurring plant alkaloid derivative to relax the bladder with opioid analgesia. B&O suppositories have been used safely in robotic prostatectomy studies and have demonstrated diminished need for IV analgesia and improved post-op pain control [14, 15]. B&O suppositories have not been studied for pain control during urogynecologic office procedures, although they are frequently utilized in office procedure analgesia protocols.

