valid and reliable measure of pain intensity [30]. The primary outcome of our study will be determined by the patient experience objectified with the NRS. The overall goal of this study is to improve the patient experience with cost-effective evidence-based treatment.

Research Plan and Design

Study Objectives

The primary objective is to determine the effectiveness of B&O suppositories in decreasing bladder injection pain at time of BoNT injection.

Our null hypothesis: Among patients given standard analgesia for BoNT treatment of overactive bladder (OAB), neurogenic detrusor overactivity (NDO), or refractory interstitial cystitis (IC), there is no difference in bladder injection pain scores with the addition of B&O suppository when compared to placebo suppository.

H₀: Mean Δ pain during procedure in active suppository group = mean Δ pain during procedure in placebo suppository group.

Change in pain (*Mean Δ pain*) is considered to be the difference in pain from the baseline pain level after analgesia, and after the first 10 injections.

Outcomes

The primary outcome will be bladder injection pain. Pain will be measured using numeric rating scales (NRS). Participants will score their preoperative baseline pain level when they check into the clinic for their procedure (P_o). Participants will report pain 40 minutes after administration of standard analgesia and suppository (just prior to bladder injection) (P_a). This will allow calibration of our primary outcome for patients with higher levels of baseline pain not related to the procedure (using themselves as controls). They will then be asked to rate bladder pain after the first 10 injections (midpoint of the procedure) intraoperatively (P_{10}). After the procedure is completed, which would be after 20 injections, the patient will again be asked to report their pain (P_{20}).

The operational definition of our primary outcome will be calculated difference in NRS pain score prior to procedure (P_a) and midway through procedure (P_{10}): Δ pain (intraoperative pain score – preoperative pain score).

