Secondary outcomes will include: pre-analgesia pain score (P_o), post-operative pain score (P_{20}), patient intolerance to the procedure, postoperative voiding trial results (pass/fail), and post void residual (PVR) results at 2 week follow-up (measured in ml, pass/fail), and diagnosis of urinary tract infection (accepted clinical definition of acute cystitis or a positive urine culture) at 2 week follow-up. PVRs < 200ml at 2 week follow-up will be considered passing result [31].

Participants will also rate their level of satisfaction with pain control immediately after the procedure using a simple Likert scale. This will be a 4-level scale ranging from 'not at all satisfied,' 'slightly satisfied,' 'mostly satisfied,' and 'very much satisfied.'

Expected Results

Investigators believe that participants randomized to the B&O suppository group will experience less bladder pain (average pain) during the BoNT injection procedure than those that were assigned to the placebo group.

Study Type and Design

This study is a randomized, pilot trial. Clinical investigators and participants will be blinded to the randomization groups. Participants, whom have elected to receive BoNT injection therapy, will be randomized to receive either a placebo or B&O suppository prior to the procedure. Pain will be assessed prior to the procedure, during the procedure, and after the procedure.

Sample size

Sample size is calculated assuming the group receiving the B&O suppository reports an average intra-procedural pain (P_{10}) score of 4.5, and assuming the control group (placebo) reports an average intra-procedural pain (P_{10}) score of 8. The assumed standard deviation is 3. Based on a power of 0.8, the required sample size per randomization group is 13. The total sample size required to achieve a power of 0.8 for this pilot trial would be 26 (13 per group).

Randomization

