narcotics. The prescription will be provided to the compounding pharmacy, which will fill the prescription based on the pre-determined randomization scheme. The compounding pharmacy will document and deliver the pill canister matching the participant's ID number, to the clinic and provide it to the Principal Investigator to store in a locked medicinal refrigerator in a locked room until the day of the procedure. Prior to administering the suppository to the patient during the procedure, the Principal Investigator will open the pill canister and document the pill canister number and the number labeled on the suppository in the patient's medical record, and study documents. If unveiling the randomization for a participant is required, the Principal Investigator can call the data coordinator or the compounding pharmacy, and the coordinator or the lead pharmacist will reveal the participant's randomization assignment over the phone. Monthly meetings will be conducted to audit the enrollment and to ensure randomization procedures are conducted appropriately.

Statistical Analysis

Preoperative demographic variables including age, race, parity, body mass index (kg/m^2), menopausal status, smoking status, medical comorbidities, and indication for BoNT treatment (OAB vs. NDO) will be compared between active and placebo patients. Continuous variables will be compared using Student t-tests. Categorical variables will be described as frequency data (proportions & percentages) and compared using Chi-square or Fisher's exact test (when expected values in any cell are less than 5). Ordinal variables will be compared using Wilcoxon Rank Sum tests.

An intent-to-treat analysis approach will be used. Results for the active group versus the control group will be compared with paired t-tests if the data are normally distributed and with Mann-Whitney tests if the data are skewed. Regression modeling will be used to analyze the relationship between our primary outcome with the following predictor variables; active vs. placebo, indication for BoNT injection (OAB vs. NDO), demographic variables, and pain scores (before-during-after procedure). Interactions between variables will be assessed and, if significant, included in the model.

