If the study subject were to be injured as a result of study procedures (separate from the BoNT therapy), subjects will be advised to immediately contact the Principal Investigator, [name] [REDACTED] [name] will decide what type of treatment, if any, is best for the study participant at that time.

Data Collection and Protection

Data Collection Procedures

Data collection will occur after obtaining informed consent for the patient to participate in the study. Demographic data will be collected to include clinical, surgical, functional, post-procedure, charted data collected as part of routine clinical visit and standard of care (Table 4). Data will be collected on a paper form (Appendix B – Data Collection Form). Follow-up data will include newly charted clinical and functional data.

Table 4. Summary of Participant Demographic Data Collected
Date of 1st consultation
Height
Weight
Body Mass Index
Race/Ethnicity
Smoking status
Menopausal status
Diagnoses
Prior surgeries
Past medical history
Medications
Indication for BoNT injection procedure

The day of the procedure, the participant will check in at the front desk. A nurse will escort the participant back to the procedure room for preparation. The participant will be given a pain assessment form with a numeric rating scale that will ask the participant to evaluate their bladder pain prior to standard analgesia and the procedure (Appendix C – Pain Assessment Form - Po). After completing the assessment, the participant will be positioned for the procedure and will be administered standard analgesia plus active or placebo suppository (based on randomization assignment).

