Aside from suppository placement, BoNT injection protocols that are in compliance with best practices established by Allergan® and the FDA will be followed. In summary, BoNT will be reconstituted in 10ml normal saline and injected in 1/2ml increments (20 injections). Standard analgesia consists of bladder instillation with 50-60ml of 1% lidocaine solution with 10ml of sodium bicarbonate. Instillation is maintained for 40 minutes prior to the procedure. During that time, the patient will rotate while on procedure table (10 minutes on supine, 10 minutes prone, 10 on each side) to maximize bladder wall contact with anesthetic. The patient will then be placed in lithotomy position for cystoscopic injection of BoNT. A 17 french 30 degree cystoscope will be used. Injection will be carried out using a flexible botox injection needle designed for the procedure. All patients will undergo standard screening for preoperative UTI and antibiotic prophylaxis per accepted guidelines.

After 40 minutes of receiving the analgesic and suppository, and right before the procedure, the participant will be asked to report their bladder pain using a numeric rating scale (Appendix D – Pain Assessment Form – Pa-P20).

Patients will undergo 20 total injections at time of BoNT treatment. An investigator will perform pain assessments during the procedure. During the procedure, the participant will be asked their bladder pain using the numeric rating scale after the first 10 of 20 injections performed during the procedure and after the next 10 of 20 performed during the procedure (Appendix D – Pain Assessment Form – Pa-P20).

After the procedure is completed, the participant will be asked to complete a voiding trial, and will be given a pain assessment form, answering a Likert scale question regarding their satisfaction with their pain management during the procedure (Appendix E – Pain Assessment Form - Post BoNT). After the voiding trial is completed and the Principal Investigator has provided standard medical counseling and care after the procedure, the participant is released from the clinic.

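### The primary outcome P_10 − P_a uses a baseline scored after the randomised suppository, the sample size was worked out for P_10 alone, and the regression lists post-dose pain scores as predictors

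*Combined protocol and SAP*

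**What the plan says.** Four numeric pain ratings are taken: P_o at check-in, P_a before injection, P_10 after ten injections and P_20 after twenty.

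- **Primary outcome (Outcomes).** "The operational definition of our primary outcome will be calculated difference in NRS pain score prior to procedure" (P_a) and midway through it (P_10). The null hypothesis in Study Objectives is stated on this change.
- **Timing of P_a.** Outcomes: "Participants will report pain 40 minutes after administration of standard analgesia and suppository (just prior to bladder injection". Data Collection Procedures agrees: "After 40 minutes of receiving the analgesic and suppository, and right before the procedure". Outcomes presents P_a as a way to calibrate for pre-existing pain that has nothing to do with the procedure.
- **Timing of P_o.** On this form patients "evaluate their bladder pain prior to standard analgesia and the procedure". It is a secondary outcome and is not part of the primary one.
- **Expected Results.** The active group "will experience less bladder pain (average pain) during the BoNT injection procedure".
- **Sample size.** "Sample size is calculated assuming the group receiving the B&O suppository reports an average intra-procedural pain" (P_10) of 4.5, against 8 on placebo, with SD 3 and power 0.8, giving 13 per group and 26 in total.
- **Regression (Statistical Analysis).** The primary outcome is modelled on treatment, indication, demographic variables "and pain scores (before-during-after procedure").

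**The concern.** Three parts of the plan do not fit together.

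1. **The baseline is post-treatment.** P_a follows the suppository by 40 minutes, so it can itself respond to treatment. The effect on P_10 − P_a equals the effect on P_10 minus the effect on P_a. A drug that lowered both scores equally would show no benefit. The plan's own rationale makes some effect at P_a plausible: these suppositories "have been commonly administered to treat spastic lower urinary tract pain", patients with refractory interstitial cystitis are eligible, and the 40-minute lead is meant to have the drug working when injection starts.
2. **The regression conditions on the outcome's own components.** P_a, P_10 and P_20 are all post-dose, and P_a and P_10 make up the outcome.
3. **Power was worked out for another variable.** The means behind 13 per group are P_10 means; the hypothesis is on the change.

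At stake is whether a null result in 26 patients, with no allowance for dropout, could be interpreted, and whether the adjusted model estimates the treatment effect at all.

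**Working it through.** **Inputs from the documents.** P_10 means 4.5 and 8 (difference 3.5), SD 3, power 0.8 and 13 per group (Sample size); two-sided tests at 0.05 (Statistical Analysis); equal allocation (Randomization).

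**Inputs the documents do not give, assumed here.** The SD of P_a (s), its correlation with P_10 (ρ), and the drug's reduction of P_a (x).

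**1. The plan's own figure.** Two-sample t-test, noncentral t, 24 df. Noncentrality = 3.5 / (3 × √(2/13)) = 2.97. Power is 0.814 at 13 per group and 0.780 at 12. So 13 per group is right for P_10.

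**2. The defined outcome, no drug effect on P_a (x = 0).** SD of the difference = √(9 + s² − 6ρs), with the effect still 3.5. Power at 13 per group, with the number per group for power 0.8 in brackets:

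| s | ρ = 0 | ρ = 0.3 | ρ = 0.5 | ρ = 0.7 |
|---|---|---|---|---|
| 1.5 | 0.72 (16) | 0.83 (12) | 0.91 (10) | 0.97 (8) |
| 2 | 0.66 (18) | 0.80 (14) | 0.90 (11) | 0.98 (7) |
| 3 | 0.52 (25) | 0.68 (18) | 0.81 (13) | 0.96 (9) |

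The lowest value comes from SD √18 = 4.24, the highest from SD √4.6 = 2.14. The planned 0.81 is recovered only when the SD of the difference is itself 3, for example s = 3 with ρ = 0.5.

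**3. The defined outcome, drug lowers P_a by x.** Effect = 3.5 − x, SD of the difference held at 3.

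| x | Measured effect | Power at 13 per group | Per group for 0.8 |
|---|---|---|---|
| 0.5 | 3.0 | 0.69 | 17 |
| 1 | 2.5 | 0.53 | 24 |
| 1.5 | 2.0 | 0.37 | 37 |

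**4. The regression.** Take a linear model for P_10 − P_a.

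- *P_a and P_10 both entered.* The outcome is exactly (+1) × P_10 + (−1) × P_a. The fit is perfect and the treatment coefficient is 0 whatever the data. A least-squares fit to 26 simulated patients confirmed this to rounding error.
- *P_10 only* (no effect on P_a). Within-arm slope on P_10 = 1 − ρs/3. Treatment coefficient = −3.5 × (1 − slope) = −3.5 × ρs/3. Over the grid in step 2 this runs from 0 to −2.45 (ρ = 0.7, s = 3), against a true −3.5.
- *P_20 only* (assumed: SD 3, correlation 0.7 with P_10, same drug effect on both, none on P_a, P_a equally correlated with both). Slope = 0.7 − ρs/3. Coefficient = −3.5 × (0.3 + ρs/3), from −1.05 (ρ = 0) to −3.5 (ρ = 0.7, s = 3).

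**5. The alternative: P_10 adjusted for P_o.** Power at 13 per group from 40,000 simulated trials for each correlation between P_o and P_10, 23 df: about 0.80 at correlation 0, 0.83 at 0.3 and 0.89 at 0.5. The approximation with residual SD 3√(1 − ρ²), where ρ is now the P_o–P_10 correlation, ignores chance imbalance in P_o and gives 0.81, 0.85 and 0.91.

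**The case against.** The strongest reply is that the injection-specific increment was chosen on purpose. Study Objectives defines the change from the post-analgesia level and states the null on it, so subtracting P_a is the definition rather than an error. The randomised comparison is valid, and type I error is not inflated if the drug does nothing. This stands as far as it goes: the increment is a legitimate question. But it is not the lower pain during the procedure that Expected Results predicts, it is not the variable named in the sample size, and P_a cannot serve as a treatment-free calibration.

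The size of the loss is also assumed. Both arms receive 40 minutes of intravesical lidocaine before P_a, and overactive bladder and neurogenic detrusor overactivity are not described mainly as painful, so P_a may sit near zero with little room to fall. That stands. A floor would also make P_a less variable: with no drug effect on it, power is 0.77 to 0.94 at s = 1 and 0.80 to 0.89 at s = 0.5. Eight of the twelve cells in step 2 are at about 0.80 or more. The SD sentence names no variable, so if SD 3 was meant for the change and P_a is equal between arms, 13 per group is right. The plan states neither condition.

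On the regression, the separate two-group comparison is untouched, the text does not say that all scores enter together, and the model form is unspecified, since some listed diagnostics belong to binary outcomes. The coefficients in step 4 are therefore conditional on a linear model. The predictor list as written still permits the degenerate fit.

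The trial is called a pilot, but it states a formal null, a power of 0.8 and a 0.05 threshold.

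**Conclusion.** The concern holds in all three parts. The documents place P_a after the randomised drug. They power P_10 while testing P_10 − P_a. They list components of the outcome among its predictors.

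The measured benefit is understated by exactly the drug's effect on P_a, which is zero if the arms do not differ there and cannot be sized from the documents. The 0.8 power is unsupported for the stated hypothesis rather than shown to be too low: it is 0.52 to 0.98 with no effect on P_a, and 0.69 to 0.37 if P_a falls by 0.5 to 1.5 points with an SD of the difference of 3. A regression with post-dose pain scores as predictors does not estimate the total treatment effect; with P_a and P_10 both in a linear model, its treatment coefficient is zero by construction. This should be settled before the primary analysis is fixed.

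**What to change.** - Make P_10 the primary outcome, as the sample size already assumes, and restate the null on it. Analyse it by ANCOVA with treatment and the pre-dose score P_o.
- Report P_10 − P_a as a secondary measure of the increment due to injection.
- In any model meant to estimate the treatment effect, allow only P_o among the pain scores; remove P_a, P_10 and P_20.
- If the sponsor prefers to keep P_10 − P_a as primary, state that the target is the injection-specific increment, redo the power with an expected effect and SD for that difference, and report P_a by arm. The restriction on predictors applies either way.

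Cost: all four scores are already collected, so there is no new measurement and no change in numbers for the P_10 option. It uses one degree of freedom and keeps power at about 0.80 or better. Both IRBs must approve the amendment before it takes effect, under the plan's own rule on protocol changes. Keeping P_10 − P_a may require a larger sample, depending on the SD and the effect on P_a.

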The antimuscarinic (anticholinergic) effects of belladonna alkaloid are dose dependent and include relaxation of smooth muscle, bronchodilation, pupil dilation, decreased gastric motility, transient tachycardia, and, most significant for this study, decreased tone and amplitude of ureteral and bladder contractions. B&O suppositories pair the belladonna anti-spasmodic with analgesia of an opioid to minimize discomfort associated with ureteral spasm. B&O suppositories have been used safely in robot assisted laparoscopic prostatectomy studies [15]. Administration of B&O suppositories prior to urologic procedures has been shown to decrease IV pain medication requirements and overall pain postoperatively [14]. The common B&O suppository formulation contains 16.2mg Bella Donna and 30 or 60 mg of opium and may be dosed as 1 suppository 1-4 times a day. The cost of this medication is approximately \$400 for 12 tabs.

Contraindications to this medication include hypersensitivity to belladonna, opiate, or any component of the formulation; glaucoma; severe renal or hepatic disease; bronchial asthma; respiratory depression; convulsive disorders; acute alcoholism; premature labor. Adverse reactions occur with an undefined frequency but may include palpitations, dizziness, drowsiness, pruritus, urticarial, constipation, nausea/vomiting, xerostomia, urinary retention, blurred vision, photophobia. The anti-cholinergic effect of BoNT, when therapy administration is closely monitored, is not likely since a single B&O dose will have worn off long before the 2-4 week onset period of BoNT is complete. Minimal systemic effect has been noted with suppository administration. Additionally, patients undergoing this therapy have theoretically already withstood an anticholinergic trial as a first line treatment for OAB/NB [28, 29].

Study Rationale

Data are lacking to demonstrate the ideal pain control regimen during office injections of BoNT. This is likely due to the relatively new application of this procedure in office. One study comparing average pain during intravesicle injections with use of alkalized lidocaine vs lidocaine gel demonstrated no result [13]. Additionally, it is difficult to accurately represent the patient pain experience. The Numeric Rating Scale (NRS) is a

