Potential confounding factors will be considered and treated appropriately during the statistical analysis. Additional confounding factors such as variability in pain and narcotic usage will be discussed in the manuscript. Investigators do not anticipate potential confounders will significantly affect the results of the study.

Standard of Care Procedures

All participants will receive injection with BoNT (Botox, Allergan) as standard clinical care. OAB participants will receive 100 units and NDO participants will receive 200 units per FDA guidelines. All participants will also undergo standard recommended preoperative analgesia per manufacture guidelines, intravesical instillation of 2% lidocaine (60ml) + sodium bicarbonate (10ml), administered 40 minutes prior to cystoscopic bladder injection. Viscous lidocaine will be used to anesthetize the urethra.

BoNT will be prepared and injected per manufacturer guidelines. After reconstitution in 10ml of normal saline, BoNT is injection in 0.5ml increments (20 injections total) into the detrusor muscle layer of the bladder dome in a standardized square pattern (Figure 1). Injection pattern will also not differ from clinical standard practice, and all patients receive the same, trigone sparing injection pattern [32].

Figure 1. Bladder injection pattern.

Regardless of participation, patients will undergo the injection procedure with BoNT, and will receive the analgesia per standard of care, both of which will be billed to the patient's insurance company. Costs associated with the BoNT therapy, including the in-office procedure visit, follow-up visit, physician fees, bladder testing conducted during two weeks follow-up, and any additional follow-up care, will be billed to the patient's insurance company, or will be the responsibility of the patient.

Information regarding volume of BoNT used in the procedure, as well as analgesia information will be collected for research purposes. Voiding trial samples, if clean, will be discarded as standard office procedures. If an infection is present, the sample is sent to the lab as standard office procedures required for appropriate medical management.

Research Intervention

Participants randomized to the active group will receive a rectal belladonna & opiate (B&O) suppository along with standard analgesia 40 minutes prior to bladder injection.

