A sample from each batch of compounded suppositories will be sent off for third-party testing to test the suppositories for chemical validity.

Participant Timeline

The length of participation in this study will be approximately two weeks from the day of the injection procedure. Table 2 illustrates the procedures or tasks to be completed during each appointment.

Table 2. ROBIN Trial Participant Timeline	
Appointment	Task/Objective
Patient Consents to Undergo Bladder Injection Therapy	
 • Patient elects to receive BoNT therapy as standard of care treatment for overactive bladder, neurogenic detrusor overactivity, or refractory interstitial cystitis • If patient meets inclusion criteria, patient is consented and offered enrollment into the study • Participant receives a participant ID number based on sequential numbering • Principal Investigator completes prescription and sends to compounding pharmacy to fill based on participant ID number
Day Prior to Procedure	
 • If informed consent is obtained, the blinded suppository will be hand delivered to the clinic by the compounding pharmacy • The suppository will be locked in a medicinal refrigerator until time of the procedure
Day of Procedure	
 • Participant checks in for procedure, and completes pain assessment (P_0) • Principal Investigator administers the suppository or placebo to the participant • Participant completes pain assessment after receiving analgesia for the procedure (P_a) • Participant undergoes BoNT procedure and completes pain assessment (P_{10}, P_{20}) • Participant completes voiding residual trial • Adverse effects or serious events are assessed • Participant is released from clinic
2-weeks follow-up visit	
 • Participant completes voiding residual trial and adverse effects or serious events are assessed • Participant receives \$25 gift card incentive for completing the study

Risks to Subjects

Because the patient has already given consent to receive the BoNT therapy, any risks associated with the procedure while participating in this study are within normal bounds for any patient electing to undergo the procedure. Overall, the risks involving the use of the B&O suppository are comparable to not utilizing it during the BoNT therapy

procedure. Use of this particular suppository should not significantly increase or decrease risks to the patient.

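### The procedure-day voiding outcome, the emptying measure the suppository can plausibly affect, is listed only as pass/fail; list its residual in ml as well

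*Combined protocol and SAP*

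**What the plan says.** The Outcomes section lists, among the secondary outcomes, "postoperative voiding trial results (pass/fail), and post void residual (PVR) results at 2 week follow-up (measured in ml, pass/fail"). One sentence therefore gives the 2-week visit two scales and the procedure day one. The only threshold is tied to the later visit: "PVRs < 200ml at 2 week follow-up will be considered passing result". No criterion is given for passing on the procedure day.

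Other sections bear on this:

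- **Research Intervention:** active participants receive the "suppository along with standard analgesia 40 minutes prior to bladder injection"; placebo participants receive an inactive suppository at the same time.
- **Data Collection Procedures:** the voiding trial follows the injections and comes before release from clinic.
- **Background, on the suppository's effects:** "most significant for this study, decreased tone and amplitude of ureteral and bladder contractions". The adverse reactions listed include "constipation, nausea/vomiting, xerostomia, urinary retention, blurred vision, photophobia".
- **Background, on duration:** "a single B&O dose will have worn off long before the 2-4 week onset period of BoNT is complete".
- **Participant Timeline, Table 2:** the procedure-day entry reads "Participant completes voiding residual trial", and the 2-week entry uses the same name for the test.

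**The concern.** The only randomised difference is one suppository, and both arms receive BoNT. On the protocol's own pharmacology, the suppository can plausibly alter bladder emptying on the procedure day. By 2 weeks BoNT is beginning to act, and a single earlier dose should contribute little. The outcome list nevertheless keeps volume for the later visit and reduces the earlier one to a binary with no written definition.

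What is at stake is how much the trial can say about retention as a suppository effect. The Risks to Subjects section expects no material change in risk from the suppository, and retention is a direct way to examine that. With 13 per arm, a pass/fail comparison discards much of the little information available. It also leaves a later trial without the residual mean and SD it would need to plan a retention endpoint.

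**Working it through.** **Inputs from the documents.** 13 per group (Sample size). Two-sided tests at 0.05, and Mann-Whitney for skewed data (Statistical Analysis). Fisher's exact test is named there for sparse categorical baseline data; I assume it for the pass/fail outcome too.

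**Inputs the documents do not give.** The SD of the residual and the procedure-day failure rate. I work in SD units and take placebo failure rates of 5%, 10% and 20%. For orientation only, the Background quotes retention in 6-17% after BoNT, over days to weeks rather than on the procedure day.

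**Step 1: the plan's own figure.** Pain difference 8 − 4.5 = 3.5, SD 3, so d = 3.5/3 = 1.167. A two-sample t-test with power 0.80 needs 12.57, that is 13 per group; power at 13 is 0.814. The stated sample size reproduces.

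**Step 2: residual analysed in ml.** Two-sample t-test, 13 v 13, normal residuals with equal SD:

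- shift 0.8 SD: power 0.499
- shift 1.0 SD: power 0.687
- power 0.80 requires a shift of 1.145 SD

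**Step 3: the same shift cut to pass/fail.** If a proportion p1 of placebo participants lie above the cut-off, a shift of δ SD gives an active failure rate p2 = Φ(Φ⁻¹(p1) + δ). For p1 = 10% and δ = 1: Φ(−1.282 + 1) = Φ(−0.282) = 38.9%. Power is the exact Fisher power, summed over all outcomes with 13 v 13.

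| Placebo failure | p2 at 1.0 SD | Fisher power, 1.0 SD | Fisher power, 0.8 SD |
|---|---|---|---|
| 5% | 26.0% | 0.130 | 0.053 |
| 10% | 38.9% | 0.255 | 0.135 |
| 20% | 56.3% | 0.380 | 0.227 |
| *t-test in ml* | | *0.687* | *0.499* |

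**Step 4: what pass/fail needs to reach significance.** The smallest significant splits at 13 v 13 are 0 v 5 failures (p = 0.039), 1 v 7 (p = 0.030) and 2 v 8 (p = 0.041). For 80% power the active failure rate must reach about 59% if placebo is 6%, 65% if placebo is 10%, or 73% if placebo is 17%.

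**Step 5: skewed residuals.** With lognormal residuals (log-SD 1 assumed) and a 1 SD shift on the log scale, simulated power is about 0.48 for a t-test on raw ml and about 0.64 for Mann-Whitney. Pass/fail powers are as in Step 3, because a monotone transformation does not change who exceeds the cut-off.

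**Step 6: what ml still cannot do.** The 95% confidence interval for a mean difference has half-width t(0.975, 24) × √(2/13) = 2.064 × 0.392 = 0.81 SD. A shift of 0.5 SD has power of only 0.23.

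**The case against.** Several points on the other side stand.

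- **Duration.** A reader might infer that the protocol declares the dose spent at 2 weeks. It does not: the sentence concerns overlap with BoNT, whose onset period runs to 4 weeks. Little suppository effect at 2 weeks is a reasonable inference for a single dose, but it is an inference.
- **Recording.** A reader might infer that no procedure-day volume is recorded. That is not established. Table 2 calls the test a residual trial on both days, and the data forms are listed in the Appendices by title only. The finding concerns the outcome definition.
- **Power model.** Normal residuals with a uniform shift favour ml. Table 1 bars a residual above 200 ml only in patients who do not routinely self-catheterise, so some participants may have high residuals. Suppose 20% sit 4 SD higher and are unaffected by the drug. Simulated power for a 1 SD shift in the rest is then about 0.22 (t-test) or 0.30 (Mann-Whitney), and pass/fail gives about 0.08, 0.15 or 0.24 with cut-offs that 5%, 10% or 20% of the others exceed under placebo. The gain narrows, and on the t-test it can vanish.
- **Sample size.** With 26 participants in a pilot powered on pain, neither scale detects a modest effect.
- **Measurement.** The bladder has just held lidocaine-bicarbonate solution and undergone cystoscopy, and no starting volume or voiding-trial method is given. A volume in ml is useful only if obtained uniformly.
- **Other safety capture.** Adverse Event Assessment and Reporting also assesses events after the suppository and during the voiding trial, with Clavien-Dindo grading. Acute retention would not pass unseen.

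It is also fair that nothing in the plan presents the 2-week PVR as a test of the suppository or says that a null voiding result will be taken as reassurance. Removing the 2-week comparison would be a preference, not a needed correction.

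None of this supplies a reason to omit the procedure-day volume from the outcome list.

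**Conclusion.** The point holds in a limited form. The Outcomes section reduces to an undefined binary the emptying measure that the suppository can plausibly affect, and lists volume only for a visit where its effect is probably small. Under normal residuals at 13 per arm, a 1 SD rise is detected with power of about 0.69 in ml against 0.13 to 0.38 as pass/fail. The advantage survives lognormal skew with Mann-Whitney (about 0.64), but shrinks if a subgroup has high residuals that the drug does not alter.

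All these figures rest on an assumed distribution and failure rate, and 1 SD cannot be converted to ml from the documents. It would go too far to say that dichotomising alone prevents the trial from detecting retention, or that ml would cure it: sample size is a main cause, and 80% power in ml still needs about 1.15 SD. A null result is inconclusive on either scale. This is a worthwhile, inexpensive improvement to a secondary safety outcome, and the primary pain analysis is untouched.

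**What to change.** In the Outcomes section, list the procedure-day voiding residual in ml alongside pass/fail. State that it is obtained by the same method in all participants, and write down the pass criterion in use that day. Make the between-arm difference in that residual, with a confidence interval, the main comparison of suppository-related retention, using Mann-Whitney if the data are skewed. Keep the 2-week PVR as listed, and say that it will be interpreted mainly as BoNT follow-up safety.

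The cost is one number on the form from a test already scheduled, a sentence on how it is measured, and slightly more analysis. If the volume is already charted, only the outcome wording and the analysis change.
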